## SYNOPSIS

Title: A Phase I/II Open-Label Multicenter Study to Evaluate the Safety and Efficacy of AK-01 as Monotherapy in Patients with Locally Advanced or Metastatic Solid Tumors
Phase of Development: Phase I/II
Name of Investigational Medicinal Product: AK-01
Objectives: Phase I The primary objective is: 

• To determine the maximum tolerated dose (MTD) of AK-01 as monotherapy in patients with locally advanced or metastatic solid tumors.

 The secondary objective is: 

• To evaluate the tolerability and overall safety profile of AK-01.

 The exploratory objectives are: 

• To evaluate the pharmacokinetic (PK) and pharmacodynamic (PD) characteristics of AK-01.

• To compare PD markers of AK-01 target engagement in tumor biopsies.

• To assess preliminary evidence of AK-01 anti-tumor activity.

 Phase II The primary objective is: 

• To evaluate the objective response rate (ORR) of AK-01 in up to 4 cohorts of locally advanced or metastatic solid tumor types of interest.

 The secondary objectives are: 

• To evaluate the tolerability and overall safety profile of AK-01.

• To evaluate the PK and PD characteristics of AK-01.

 The exploratory objectives are: 

• To evaluate the effect of AK-01 on other clinical endpoints in these indications.

• To evaluate the efficacy of AK-01 in patients with locally advanced or metastatic solid tumor types of interest with different molecular profiles.

**Study Design:**

This open-label, non-randomized, multi-center study will explore the dose-limiting toxicities (DLTs), MTD, safety, PK, PD, and efficacy of AK-01 in patients with locally advanced or metastatic solid tumors. In the Phase I dose escalation part of this study, patients with solid tumors (excluding primary brain tumors) will receive AK-01 twice daily in cycles of 21 days in a multiple ascending dose (MAD) schedule in order to determine the MTD. Dose escalation will follow a 3 + 3 design. AK-01 target engagement will be explored in tumor biopsies. In the Phase II part of this study, AK-01 will be administered to patients in 2 cohorts of locally advanced or metastatic solid tumors of interest: small-cell lung cancer (SCLC) and hormone positive/human epidermal growth factor receptor 2 (HER2)-negative breast cancer (BC). Subsequently, at the sponsor's discretion, patients with the following tumor types may be enrolled in up to 2 additional cohorts: triple negative- breast cancer (TNBC), squamous cell cancers of the head neck (SCC-HN) and/or any other tumor type (OT) that warrants further exploration. Tumor response will be measured using Response Evaluation Criteria in Solid Tumors (RECIST) v.1.1. Dosing of AK-01 may continue until disease progression if the patient is receiving benefit and experiencing no severe toxicity in the opinion of the investigator.

**Patient Population:**

Patients with locally advanced or metastatic solid tumors will be enrolled in Phase I. In Phase II, initially patients with locally advanced or metastatic solid tumors of interest, such as SCLC and BC will be enrolled. Subsequently, at the sponsor's discretion, patients with TNBC, SCC-HN and/or one other solid tumor type.

**Number of Patients:**

In Phase I, up to 30 patients may be enrolled. In Phase II, up to 30 patients will be enrolled in each cohort, for a total of up to 120 patients.

**Main Eligibility Criteria:**

Male or female patients  $\geq 18$  years of age will be eligible if they meet the following criteria:

- Performance status of 0 or 1 on the Eastern Cooperative Oncology Group (ECOG) scale.
- Estimated life expectancy of  $\geq 12$  weeks.
- Adequate organ function.
- Have failed a minimum of 1 but no more than 4 regimens for locally advanced or metastatic disease.
- Reliable and willing to make themselves available for the duration of the study, and willing to follow study procedures.
- Locally advanced or metastatic solid tumors:
  - Phase I – All-comer evaluable tumors (excluding brain tumors).
  - Phase II – Tumors measurable by RECIST:
    - 1) SCLC having failed platinum-based therapy but be in a platinum sensitive relapse (having responded to up to 6 cycles of platinum therapy with at least SD, PR, or CR, and then maintained that response without progression for 3 months after the last platinum dose. Patients could have received maintenance therapy following the completion of platinum therapy. Patients who never responded or progresses  $< 3$  months after the last platinum dose are not eligible);

- 2) estrogen receptor (ER+) and/or progesterone receptor (PR+) positive/HER2-negative BC having failed a hormone therapy and a CDK4/6 inhibitor. Patients may have failed up to 2 chemotherapy regimens and unlimited hormonal or other kinase therapies;
  - 3) relapsed/resistant TNBC;
  - 4) relapsed/refractory human papilloma virus (HPV) associated squamous cell cancers of the head and neck; and/or
  - 5) other tumor type that warrants further exploration.
- No history of clinically significant cardiac disease.

**Study Treatment:**

In Phase II, AK-01 will be supplied as 25 mg capsules to be administered orally twice daily (BID) in cycles of 21 days. Patients will be encouraged to fast at least 1 hour before and following dosing. Dose reduction and/or interruption for any given patient will be permitted for toxicity throughout the study.

**Statistical Methods:**

Sample Size: In Phase I, the 3 + 3 design dose escalates cohorts of up to 9 patients in groups of a minimum of 3 until the MTD is identified: the dose immediately below the dose at which  $\geq 2/3$ ,  $\geq 2/6$ , or  $\geq 3/9$  patients in a cohort experience a DLT during the first 21 days of treatment (Cycle 1). Up to 6 additional patients may be dosed at or below the MTD to gain additional information for determining the phase II dose (P2D). A sample size of up to 30 patients is considered sufficient to identify the MTD in Phase I; this is not powered on the basis of statistical hypothesis testing. In Phase II, up to 30 patients for each tumor type will be administered study treatment. Whenever the true ORR is at least 20% for the study treatment, a sample size of 15 to 20 patients per tumor type provides approximately 60% power to reject the null hypothesis.

PK: The primary PK parameters will be estimated using noncompartmental analysis, and will include the area under the AK-01 plasma concentration-time curve from time zero to 12 hours post-dose ( $AUC_{0-12}$ ) and to 24 hours post-dose ( $AUC_{0-24}$ ), the peak concentration ( $C_{max}$ ) and the time to  $C_{max}$  ( $t_{max}$ ). Other parameters such as apparent terminal elimination half-life ( $t_{1/2}$ ), apparent total plasma clearance (CL/F) and apparent volume of distribution ( $V_z/F$ ) will also be calculated. PK parameters will be calculated individually and presented by summary statistics.

PD and PK/PD: Changes in hematology measures (white blood cell count, neutrophil count, and lymphocyte count) will be explored; the relationship between hematological changes and AK-01 PK may be evaluated. Markers of dose-dependent target engagement (phospho-histone H3 and/or markers of apoptosis, phosphorylation, DNA damage, mitosis) will be evaluated, compared across time points, and compared between tumor biopsy samples. The inhibition of Aurora A kinase and Aurora B kinase by AK-01 may be compared. Additional PK and PD parameters may be calculated, and further PK/PD analyses may be conducted.

Safety: Safety assessments will include clinical laboratory evaluations (hematology, clinical chemistry, endocrinology, and urinalysis), assessment of ECOG status, electrocardiogram, vital signs, pregnancy test(s), adverse event (AE) recording, and AE grading by National Cancer Institute Common Terminology Criteria for Adverse Events version 4.03 (NCI CTCAE). Dose-limiting toxicities and the results of safety assessments will be summarized using descriptive statistics. The relationship between ECG parameters and AK-01 exposure may be explored.

Efficacy: The primary assessment of efficacy in Phase II will be based on the ORR, which will be compared to 5% using a test of a single proportion. RECIST v.1.1 criteria will be used to determine the effect of AK-01 on tumor burden. ORR, duration of objective response, best response on study,

progression-free survival, overall survival, and disease control rate may be summarized with descriptive statistics; additional efficacy parameters may be calculated.

Molecular Profile: Molecular profiles predictive of tumor response to AK-01 may be explored in tumor tissue and blood (i.e., somatic mutations). Measures of efficacy may be compared in patients with different molecular tumor profiles.

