### 3.6. Determination of Sample Size

In Phase I, the 3 + 3 design dose escalates cohorts of up to 9 patients until the MTD is identified. Up to 6 additional patients may be dosed to inform the selection of a P2D. A sample size of approximately 30 patients was considered sufficient to identify the MTD and is not powered on the basis of statistical hypothesis testing.

In Phase II, up to 30 patients for each tumor type will be administered IMP (up to 120 patients total). An observed ORR (proportion of partial or complete responders by RECIST) of  $\geq 20\%$  with

a durability of at least 4 months will be considered evidence of efficacy. With 15 patients in a cohort, there is approximately 60% power to reject the null hypothesis of the ORR being  $\leq 5\%$  when the true ORR is 20% using a one-sided exact test for a single proportion at a significance level of 0.05. The power for this statistical test for a single tumor type without any adjustment for multiplicity is provided in [Table 2](#) using various observed ORRs.

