**Table 2. Statistical Power of Observed Overall Response Rates**

True ORR	10%	15%	20%	25%	30%
N=15	18%	40%	60%	76%	87%
N=20	13%	35%	59%	78%	89%

Thus, whenever the true ORR is at least 20%, a sample size of 15 or 20 patients per tumor type provides approximately 60% power to reject the null hypothesis.

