#### *8.1.6. Efficacy Analysis*

The primary assessment of efficacy in Phase II will be based on the ORR, which will be compared to 5% using a test of a single proportion. RECIST v.1.1 criteria will be used to determine the effect of AK-01 on tumor burden. ORR, duration of objective response, best response on study, progression-free survival, overall survival, and disease control rate may be summarized with descriptive statistics. The rate of disease control (stable disease, partial response, or complete response assessed by RECIST v. 1.1 in 2 consecutive scans) may be summarized by tumor type, as appropriate. Descriptive statistics will be used to analyze all tabulated efficacy data. Progression-free survival (PFS) and OS curves may be estimated using Kaplan-Meier methods.

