## 9.2. Determination of Sample Size

See the Protocol, Section 3.6.

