## 9.6. Analyses of Efficacy

### 9.6.1. Phase II Primary Objective

The primary endpoint of phase II is ORR. The primary statistical hypotheses

$$H_0: \text{ORR} \leq 0.05$$

will be tested against an alternative

$$H_A: \text{ORR} > 0.05$$

by the means of a one-sided exact binomial test for a single proportion at a significance level of 0.05. See Section 9.3.1 for details on the statistical test. No multiple testing adjustment will be applied. The ORR will be presented with an exact one-sided 95% confidence interval (Clopper & Pearson). The analysis will be performed in the FAS as well as in Efficacy evaluable analysis set. That means, if the analysis set includes patients with missing baseline assessments, non-measurable disease at baseline (though this would be a protocol deviation) or no evaluable post-baseline

assessments, they will be counted in the denominator and not in the numerator. The ORR will be summarized and tested by cohort.

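### The Synopsis claims about 60% power for 15 to 20 patients per cohort; at a true ORR of 20% the plan's exact test gives only 45% to 55% at 17, 18 and 19 patients

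*Protocol*

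**What the plan says.** The Synopsis, under Statistical Methods, sets the condition that the true ORR is at least 20% and then states that "a sample size of 15 to 20 patients per tumor type provides approximately 60% power to reject the null hypothesis".

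Protocol Section 3.6 repeats the sentence below Table 2 with one word changed: "a sample size of 15 or 20 patients per tumor type provides approximately 60% power to reject the null hypothesis". Table 2 has rows for N=15 and N=20 only; at a true ORR of 20% it prints 60% and 59%.

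The test behind these figures is fixed. Section 3.6 sets the null hypothesis at an ORR of 5% or less and calculates power "using a one-sided exact test for a single proportion at a significance level of 0.05". SAP Section 9.6.1 plans the same test, by cohort and without multiplicity adjustment. For sample size the SAP says only "See the Protocol, Section 3.6".

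Cohort size has a ceiling but no fixed value: "In Phase II, up to 30 patients for each tumor type will be administered IMP (up to 120 patients total").

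**The concern.** The Synopsis turns a statement about two tabulated sizes into one about every size between them. An exact binomial test does not allow that step. The critical number of responders is an integer, and when it goes up by one the attained significance level and the power both fall sharply. Power can therefore be near 60% at both ends of a range and well below it inside.

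A cohort could be analysed at 17 to 19 patients. Nothing fixes its size below the ceiling of 30. SAP Section 9.6.1 also says of the ORR test: "The analysis will be performed in the FAS as well as in Efficacy evaluable analysis set". A cohort that treats 20 patients could therefore have 17 to 19 in the second set. Someone relying on the Synopsis would then credit the test with more power than it has, and might give a non-significant result too much weight as evidence of inactivity.

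**Working it through.** **Inputs**

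- Null ORR p0 = 0.05 (Protocol Sections 3.6 and 8.1.6; SAP Section 9.6.1).
- True ORR p1 = 0.20. The Synopsis says at least 20%; power rises with the true ORR, so 20% is the least favourable case and the one to check.
- One-sided exact binomial test at level 0.05 (Protocol Section 3.6; SAP Sections 9.3.1 and 9.6.1).
- N = 15 to 20 (Synopsis).

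**Formulas**

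For X ~ Binomial(N, p), P(X ≥ r | p) = 1 − Σ C(N,k) p^k (1−p)^(N−k), summed over k = 0 to r−1.

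- Critical value r: the smallest r with P(X ≥ r | 0.05) ≤ 0.05.
- Attained alpha = P(X ≥ r | 0.05).
- Power = P(X ≥ r | 0.20).

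**Step 1: reproduce the plan's own figures**

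- N=15: r=3, attained alpha 3.62%, power 60.2% (Table 2: 60%).
- N=20: r=4, attained alpha 1.59%, power 58.9% (Table 2: 59%).

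All ten cells of Table 2 reproduce to within one point. Nine agree on rounding; the tenth (N=20, true ORR 25%) computes to 77.48% and is printed as 78%. So this is the test that the plan used.

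**Step 2: find where the critical value changes**

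- N=16: P(X ≥ 3 | 0.05) = 1 − (0.4401 + 0.3706 + 0.1463) = 0.0429, so 3 responders still reject.
- N=17: P(X ≥ 3 | 0.05) = 1 − (0.4181 + 0.3741 + 0.1575) = 0.0503, just above 0.05, so 4 are needed.

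**Step 3: power at N=17**

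P(X ≥ 4 | 0.20) = 1 − (0.0225 + 0.0957 + 0.1914 + 0.2393) = 0.4511. If 3 responders had still sufficed, power would have been 69.0%.

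**Step 4: the whole range, true ORR 20%**

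| N | Responders to reject | Attained alpha | Power | Difference from 60% (points) |
|---|---|---|---|---|
| 15 | ≥3 | 3.6% | 60.2% | +0.2 |
| 16 | ≥3 | 4.3% | 64.8% | +4.8 |
| 17 | ≥4 | 0.9% | 45.1% | −14.9 |
| 18 | ≥4 | 1.1% | 49.9% | −10.1 |
| 19 | ≥4 | 1.3% | 54.5% | −5.5 |
| 20 | ≥4 | 1.6% | 58.9% | −1.1 |

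Solving P(X ≥ 4 | p) = 0.60 for p gives the true ORR needed for 60% power: 23.7% at N=17, 22.4% at N=18 and 21.3% at N=19.

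**Step 5: would another reading of the test rescue the statement?**

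At N=17 to 19 and a true ORR of 20%:

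- Normal approximation: 74% to 77%.
- Normal approximation with continuity correction: 64% to 67%, and 69% at N=20, where Table 2 prints 59%.
- Mid-p version: 69% to 76%.
- Exact test at level 0.025: the same 45% to 54% as in Step 4, but only 35% at N=15, where Table 2 prints 60%.

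None gives about 60% across 15 to 20, and only the exact one-sided test at 0.05 matches Table 2.

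**The case against.** The best defence is that this is a slip in paraphrase, not a wrong calculation. The correct sentence stands in Section 3.6, Table 2 labels its rows plainly, and the SAP points there. No passage plans a cohort of 17 to 19 and no interim rule leads to one. At the ceiling of 30 patients power is 74.5%, and every size from 21 to 30 gives at least 63.0%, so power is not overstated there. At N=19, 54.5% is only modestly below about 60%.

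Most of this stands and sets the weight of the point. It does not make the Synopsis sentence true: 45% and 50% cannot pass as approximately 60%, and the documents do not exclude an analysis at those sizes.

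The Section 3.6 sentence is itself a little loose. It attaches about 60% power to any true ORR of at least 20%, while Table 2 shows 76% to 89% at 25% and 30%. Read as a floor it is acceptable, and the same reading is applied to the Synopsis here.

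**Conclusion.** The concern holds and is minor. At a true ORR of 20%, the Synopsis figure is right at N=15 and N=20, somewhat low at N=16, and too high by about 15, 10 and 5.5 points at N=17, 18 and 19. The result rests on the test and level stated in both documents and on a true ORR of exactly 20%; it needs no outside assumption. The practical effect is confined to a cohort or analysis set of 17 to 19 patients. The planned test, its error rate and the patient numbers are unaffected.

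**What to change.** In the Synopsis, change the range to the two sizes, 15 or 20, as in Section 3.6. If a range is wanted, state power of about 45% to 65% for 15 to 20 patients at a true ORR of 20%. Either is a wording change, with no effect on patient numbers, the test or its level.

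Optional, and not needed to correct the error: because cohorts may reach 30, Table 2 could be extended with critical value, attained alpha and power. At a true ORR of 20%:

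| N | Responders to reject | Attained alpha | Power |
|---|---|---|---|
| 21 | ≥4 | 1.9% | 63.0% |
| 25 | ≥4 | 3.4% | 76.6% |
| 28 | ≥4 | 4.9% | 84.0% |
| 29 | ≥5 | 1.4% | 71.6% |
| 30 | ≥5 | 1.6% | 74.5% |

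A footnote could add two things. First, the critical value follows the N of the analysis set being tested. Second, Section 3.6 also has a descriptive criterion, an observed ORR of at least 20% with "a durability of at least 4 months will be considered evidence of efficacy". Before durability is considered, the count this requires (N/5 rounded up) differs from the critical value at N=16 (4 against 3) and at every N from 21 to 30 (for example 6 against 5 at N=30). The cost is a longer table and one footnote.

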## LIST OF ABBREVIATIONS

AE	Adverse event
AUC	Area under the plasma concentration-time curve
AUC 0-12	AUC from time zero to 12 hours post-dose
AUC 0-24	AUC from time zero to 24 hours post-dose
AurA	Aurora A kinase
AurB	Aurora B kinase
ANC	Absolute neutrophil count
ALT	Alanine aminotransferase
AST	Aspartate aminotransferase
ATP	Adenosine triphosphate
BC	Breast cancer
BID	Twice a day
C	Cycle
CDK1	Cyclin-dependent kinase 1
CDK4/6	Cyclin-dependent kinase 4/6
CL/F	Apparent total plasma clearance after extravascular administration
CKD-EPI	Chronic Kidney Disease Epidemiology Collaboration
C max	Maximum observed plasma concentration
CNS	Central nervous system
eCRF	Electronic case report form
CT	Computed tomography
CTCAE	Common Terminology Criteria for Adverse Events

D	Day
DLT	Dose-limiting toxicity
DNA	Deoxyribonucleic acid
ECG	Electrocardiogram
ECOG	Eastern Cooperative Oncology Group
EDC	Electronic data capture
eGFR	Estimated glomerular filtration rate
ER +	Estrogen receptor positive
ELISA	Enzyme-linked immunosorbent assay
FSH	Follicle stimulating hormone
GCP	Good Clinical Practices
G-CSF	Granulocyte-colony stimulating factor
GI	Gastrointestinal
HIV	Human immunodeficiency virus
HER	Human epidermal growth factor receptor 2
HNSTD	Highest non-severely toxic dose
hr	Hour
ICD	Informed consent documents
ICH	International Conference on Harmonisation
IEC	Independent Ethics Committee
IMP	Investigational medicinal product
IRB	Institutional Review Board
MAD	Multiple ascending dose

mg	Milligram
min	Minute
mL	Milliliter
MRI	Magnetic resonance imaging
msec	Millisecond
MTD	Maximum tolerated dose
NCI	National Cancer Institute
ORR	Objective response rate
OS	Overall survival
PD	Pharmacodynamic
PFS	Progression-free survival
PK	Pharmacokinetic
PR +	Progesterone receptor positive
PTEN	Phosphatase and tensin homolog
QTcF	QT interval corrected for heart rate using the Fridericia formula
Rb1	Retinoblastoma protein 1
RECIST	Response Evaluation Criteria in Solid Tumors
P2D	Phase II dose
SAC	Safety Assessment Committee
SAE	Serious adverse event
SAP	Statistical analysis plan
SCLC	Small-cell lung cancer
TP53	Tumor protein p53

$t_{\max}$	Time of maximum observed concentration
$t_{1/2}$	Apparent terminal elimination half-life
TdP	Torsades de Pointes
ULN	Upper limit of normal
$V_z/F$	Apparent volume of distribution during the terminal elimination phase

## 1. INTRODUCTION

### 1.1. General Introduction

The Aurora kinases comprise a family of serine/threonine kinases that play a critical role in the mitotic process. Aurora A kinase (AurA) localizes to the centrosomes and spindle poles and recruits the cyclin B1–CDK1 complex, committing the cell to mitosis. Aurora B kinase (AurB) plays a role in chromosome condensation, regulation of kinetochore function, and cytokinesis. Amplification of the AurA gene *AURKA* is oncogenic, and has been observed in colorectal, gastric, prostate, and breast cancers; the *AURKA* Phe31Ile polymorphism is associated with an increased risk for esophageal, ovarian, lung, and breast cancers. AurA overexpression may also play a role in resistance to paclitaxel, gefitinib, and cisplatin.

Disruption of AurA activity significantly impairs mitotic progression through activation of the mitotic checkpoint. This results in defects in mitotic spindle formation and prometaphase arrest, with subsequent cell death through proapoptotic pathways. In contrast, AurB inhibition causes the cell to bypass the mitotic checkpoint, creating polyploid cells through failure of cytokinesis. Dual AurA/B or AurB-dominant kinase inhibitors allow cells to bypass the mitotic checkpoint, with antitumor activity being dependent on activation of apoptosis in response to increasing genomic instability. This AurB phenotype will dominate the AurA phenotype if inhibitors are not highly selective for AurA.

AK-01 is a reversible, ATP-competitive small molecule drug that inhibits AurA with 1000-fold selectivity over AurB in both biochemical and cell-based assays. Administration of AK-01 to mice implanted with patient-derived xenografts results in tumor growth arrest or regression in a number of tumor types. *In vitro* and *in vivo* data suggests tumors with *Rb1* loss-of-function mutations may be particularly responsive to inhibition of AurA (see Investigator's Brochure).

CCI

Further information on the known benefits and risks of AK-01 can be found in the Investigator's Brochure.

### 1.2. Rationale and Justification for the Study

Preclinical data demonstrating biologic activity *in vivo* with an acceptable safety profile supports the evaluation of AK-01 in humans.

The selectivity of AK-01 for AurA differentiates AK-01 from other inhibitors of Aurora kinases (e.g., MLN8237, AZD1152, and PHA-739358), and may allow AK-01 to elicit the benefits of AurA inhibition without triggering the adverse and often dose-limiting neutropenia associated with AurB inhibition.

The present study will evaluate the safety and efficacy of AK-01 in patients with locally advanced or metastatic solid tumors, with an emphasis on small-cell lung cancer (SCLC),

estrogen receptor (ER+) and/or progesterone receptor (PR+) positive/human epidermal growth factor receptor 2 (HER2)-negative breast cancer (BC), triplenegative- breast cancer (TNBC), human papilloma virus (HPV) associated squamous cell cancers of the head neck (SCC-HN), and any other tumor type (OT) that warrants further exploration. A large proportion of these patients bear a *Rb1* loss-of function mutation, a molecular signature which sensitized animal models to AK-01 in preclinical testing (see Investigator's Brochure). Patients are eligible for the Phase II part of this study if they have failed standard of care therapies which do not preclude therapy with an AurA inhibitor: hormone therapy and CDK4/6 inhibitor for ER+ and/or PR+/HER2-negative BC, platinum-based therapy for SCLC, relapsed/resistant TNBC, HPV associated SCC-HN, and/or any other tumor type that warrants further exploration (see Investigator's Brochure for further details).

